Whether this sleep timing intervention works in actual older night workers, as opposed to participants in lab studies, remains to be tested. We therefore will field test, in older night workers (age 50-65 years), the sleep timing intervention that we have developed in laboratory studies; we will examine the **efficacy** of this intervention in improving sleep duration and quality, as well as performance and alertness across 3 night shifts. We will also conduct a survey study among a large group of older shift workers to examine the factors that influence their ability to adopt such a schedule. Finally, we will have participants from both studies take part in focus groups where the **feasibility** and **acceptability** of the afternoon-evening sleep intervention will be examined. To evaluate the efficacy, feasibility, and acceptability of an 8-h afternoon-evening sleep schedule in the field/real world, our study will address the following Aims:

1. Test the hypothesis that older night shift workers scheduled to an 8-h afternoon-evening sleep episode will sleep longer and have fewer sleep interruptions than those randomized to an *ad lib* sleep/control condition.
2. Test the hypothesis that older night shift workers scheduled to an 8-h afternoon-evening sleep episode will show greater subjective and objective alertness on night shifts compared to those randomized to an *ad lib* sleep/control condition.
  - 2a. Conduct exploratory analyses to examine whether older night workers scheduled to an 8-h afternoon-evening sleep episode show reduced physiological stress (cortisol), reduced subjective stress and fatigue, and improved mood and quality of life compared to those randomized to an *ad lib* sleep/control condition.
  - 2b. Conduct exploratory analyses to compare an 8-h afternoon-evening sleep schedule to an 8-h free sleep

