schedule in older night shift workers for impacts on sleep duration and quality, alertness and performance, stress, subjective fatigue, mood, and quality of life, to evaluate the effect of the timing of sleep regardless of duration. 3. Test how individual factors influence the ability to adopt an 8-h sleep episode while working night shifts. In a shift worker survey, we will determine the percentage of night shift workers who report their ability to adopt an 8-h sleep schedule (regardless of timing), those who report being able to adopt an 8-h afternoon-evening sleep episode, and we will then examine how demographic (e.g., sex) and other factors (e.g., occupation) impact this adoptability in order to evaluate the *feasibility* of an 8-h afternoon-evening sleep schedule for older night workers. In debriefing focus groups, we will examine participants' perceptions of their ability to adhere to an 8-h afternoon-evening sleep schedule (*acceptability*), barriers to following such a schedule, and their willingness to adopt such a schedule outside the study for future prolonged implementation.

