The Baseline Block consists of a week during which participants work at least three consecutive 8-h night shifts. The three night shifts are preceded by a day off. All participants will be instructed to continue their normal routines, maintaining their habitual self-selected sleep-wake schedule. Sleep-wake and light exposure patterns will be recorded continuously using actigraphy, and a daily sleep e-diary will be filled in within the first hour after awakening from each main sleep episode. Performance (attention), alertness and mood will be rated three times on each night shift (just prior to their shift, on a break during their shift, and immediately after their shift). The purpose of this Baseline segment is to obtain measures of sleep duration and consolidation (to address Aim 1), alertness, mood, and performance (to address Aims 2, 2a and 2b) when working night shifts following their typical sleep routine. Immediately after the third night shift, an optional saliva sample will be taken to measure stress level (cortisol) and each participant will complete a baseline questionnaire covering questions related to fatigue, recovery, stress, and quality of life (to address Aim 2a). Participants will be given a specially configured mini iPad on which the E-diary, the performance test, alertness and mood rates, and fatigue, recovery, stress and quality of life questionnaire are programmed on.

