The Intervention Block is similar to the Baseline Block, consisting of at least three consecutive 8-h night shifts, with the participants wearing an activity monitor, maintaining a daily sleep e-diary, and rating alertness, mood and attention three times per night shift using a mini iPad provided by the investigators. At the end of the first night shift, the participant will be told about their randomization group. In the control group (Group A), participants will not be given any instructions about the timing or duration of their sleep, but will be instructed to follow their usual night shift sleep routine. In the 8-h afternoon-evening sleep intervention group (Group B), participants will be instructed to go to bed between 13:00 and 14:00 (depending on their individual commute time) and to remain in bed attempting to sleep for 8 hours (until 21:00-22:00) before the next two night shifts. In the 8-h free sleep group (Group C), participants will be instructed to remain in bed for 8 continuous hours before the next two night shifts, but will not be given any instruction regarding which 8 hours they should sleep. Immediately following the last night shift, the participant will have the option to take a saliva sample to measure their stress level (cortisol), and they will complete a follow-up questionnaire where their fatigue, recovery, stress, and quality of life will be reassessed to investigate any exploratory short-term changes resulting from the intervention schedule. After completion of the two blocks, the participant will send back the activity monitor and iPad in a prepaid secured return package by mail or an investigator will arrange to meet with the participant to retrieve the activity monitor, iPad, and cortisol sample. Within 3 months after completion of the study blocks the participant will be invited to take part in a virtual Focus Group by secure videoconferencing (via HIPAA-compliant & MGB-approved Zoom).

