## VI. BIOSTATISTICAL ANALYSIS

### VI. a) Data variables, b) Study endpoints, c) Statistical methods

**Analysis of objective sleep duration and quality, and subjective sleep quality in the Field Trial.** Sleep data will be calculated in all participants from both blocks (Baseline vs. Intervention) using actigraphy. Duration of sleep (total sleep time, TST), number of awakenings, fragmentation index (FI) during the major sleep episode and subjective sleep quality from the e-diaries may be used as outcome measures to address Aim 1. After descriptive analyses, we may use linear and generalized linear mixed models to analyze main and interaction effects for factors condition (randomization group: ad lib sleep, 8-h afternoon-evening sleep, or 8-h free sleep) and shift (Baseline: B-Night 2, B-Night 3; Intervention: I-Night 2, I-Night 3). To account for inter-individual differences, we may incorporate into our statistical model a random intercept statement allowing for means to vary between participants. We will compare within subjects (shift) and between groups (condition).

**Field Trial analysis of performance and subjective alertness (Aim 2).** Each of the tests will be administered using an iPad app. Initial processing of tests will be calculated automatically (e.g., exact time of administration, scoring of alertness scales; mean and median reaction time; number of lapses, shortest (fastest 10%) and longest (slowest 10%) reaction times on PVT]. Following the descriptive measures, analyses of RT and lapses and subjective alertness data may be performed using linear and generalized linear mixed models to analyze main and interaction effects for factors condition (randomization group, as above) and shift (as above) with participant as a random effect.

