**Exploratory analysis of subjective stress and fatigue, recovery, mood, quality of life, and physiological stress in the Field Trial (Aim 2a).** Scores of acute subjective fatigue, inter-shift recovery, subjective stress, and quality of life will be calculated from the questionnaire administered at the end of Baseline and the end of Intervention. Mood will be assessed from visual analog scales administered three times per shift on nights 2 and 3 in the Baseline and Intervention blocks. Physiological stress will be assessed by analyzing cortisol levels in the optional saliva samples collected immediately after the third night shift in the Baseline and Intervention blocks. We will compare data from the Baseline to data from the Intervention for the three groups using linear and generalized linear mixed model analysis with factors condition (randomization group) and block (Baseline or Intervention) and incorporating a random intercept statement allowing for means to vary between participants.

**Field Trial exploratory analysis of scheduled 8-h afternoon-evening sleep vs. 8-h free sleep (Aim 2b).** We may compare results described above (sleep, performance and alertness, subjective stress, fatigue, recovery, mood, quality of life, and physiological stress) between the two scheduled sleep groups to determine whether the timing of an 8-h sleep episode has a significant impact on any of the outcomes. For this analysis, data from the 8-h free sleep group will first be examined for the time of day at which it occurred. Those participants who self-selected an afternoon-evening sleep episode will be classified with the 8-h afternoon-evening sleep group. We will carry out the analyses described above using linear mixed model analysis with factors condition (randomization group) and block (Baseline or Intervention) or night, incorporating a random intercept statement allowing for means to vary between participants.

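### The Aim 2b timing analysis moves self-selected Group C participants into Group B but still calls the factor the randomisation group, so the named test is not a randomised comparison

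*Combined protocol and SAP*

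**What the plan says.** Section II describes Aim 2b as exploratory ("Conduct exploratory analyses to compare an 8-h afternoon-evening sleep schedule to an 8-h free sleep" schedule) and gives its purpose as "to evaluate the effect of the timing of sleep regardless of duration". In Section V (Intervention Block), participants learn their group at the end of the first Intervention night shift. Group B is given clock times for bed. Group C is told to stay in bed for 8 continuous hours "but will not be given any instruction regarding which 8 hours they should sleep". In the Baseline Block everyone follows their own routine, "maintaining their habitual self-selected sleep-wake schedule".

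The Aim 2b paragraph of Section VI compares the two scheduled-sleep groups on all the field-trial outcomes, worded as something the team may do. It first looks at when Group C slept. Then: "Those participants who self-selected an afternoon-evening sleep episode will be classified with the 8-h afternoon-evening sleep group". The analyses described earlier in the section are to be repeated "using linear mixed model analysis with factors condition (randomization group) and block (Baseline or Intervention) or night".

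The sleep analysis earlier in Section VI uses "factors condition (randomization group: ad lib sleep, 8-h afternoon-evening sleep, or 8-h free sleep") and plans both main and interaction effects, adding: "We will compare within subjects (shift) and between groups (condition").

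**The concern.** The two key sentences cannot both hold. Once some of Group C is counted with Group B, the factor is no longer randomisation group. If the factor is coded as randomised, the reclassification has no effect.

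B versus C is the only pair of arms in which 8 h in bed is prescribed on both sides while the timing instruction differs, so it is the trial's one randomised handle on timing. Sorting C by a choice made after assignment gives that up. Section I.a itself lists chronotype and flexibility of sleep timing among the factors that vary between workers and affect adaptation, so choosers may well differ from non-choosers.

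The rule is also incomplete in three ways:

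- **One direction only.** The Focus Group recruitment text in Section III expects some participants not to comply, but Aim 2b has no rule for Group B participants who slept outside their window.
- **No definition.** No clock-time definition of afternoon-evening sleep is given for Group C. Section V gives times for Group B only.
- **No named test.** The plan does not say which model term tests timing. This decides which differences between choosers and non-choosers cancel.

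**Working it through.** **The plan's own figure.** There is no sample-size figure for Aim 2b. Section VI.d sizes A versus B: 25 per group for 78 min of total sleep time, SD 84.4 min, alpha 0.05, 90% power (printed as beta = 0.9). Two-sided: n = 2 × (1.960 + 1.282)² × 84.4² / 78² = 24.6, so 25. This reproduces. The n and SD are carried over below.

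**Assumed, because the documents do not give them.**

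- f: the share of workers who would choose afternoon-evening sleep if left free. Randomisation makes f the same in B and C on average.
- g: how much more choosers change from Baseline than others, for reasons unrelated to timing.
- d: a stable gap between choosers and others, present in both blocks.
- Within-person correlation 0.5 (0.3 and 0.7 also tried), one value per block.

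With two balanced blocks, condition-by-block equals the difference in change from Baseline, and the condition main effect equals the difference in two-block means. Rejection rates come from simulation, 4,000 runs per scenario; repeat runs agreed to within about one percentage point.

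**1. Gap in change, no timing effect.** Mean change in B is μ + fg. The choosers in C have μ + g, and the rest of C has μ. After the move:

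- enlarged B = μ + (fg + fg)/(1 + f)
- remaining C = μ
- bias = 2fg/(1 + f)

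| f | g (min) | Bias by formula | Simulated bias | Rejection |
|---|---|---|---|---|
| 0.1 | 20 | 4/1.1 = 3.6 | 3.3 | about 5% |
| 0.2 | 40 | 16/1.2 = 13.3 | 13.6 | 8% |
| 0.4 | 60 | 48/1.4 = 34.3 | 34.5 | 22% |

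With g = 60 and correlation from 0.3 to 0.7, rejection is about 10–16% at f = 0.2 and 17–33% at f = 0.4. At f = 0.05 the bias is 2 × 0.05 × 20/1.05 = 1.9 min for g = 20 and 5.7 min for g = 60.

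**2. Stable gap, no timing effect.** On condition-by-block the gap cancels: with d = 60 and f = 0.2, bias is −0.3 min and rejection 5.2%. On the condition main effect the bias is 2fd/(1 + f). With d = 60 this is 10.9, 20.0 and 34.3 min at f = 0.1, 0.2 and 0.4, with rejection of 8%, 14% and 28%.

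**3. A real timing effect T, with choosers already in that window at Baseline.** Choosers then gain nothing from the schedule in either arm. As randomised, the contrast is (1 − f)T. After the move it is T(1 − f)/(1 + f). For T = 60:

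- f = 0.2: 48 min as randomised, 40 min after the move (rejection 48% against 34%)
- f = 0.4: 36 min as randomised, 26 min after the move

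**4. A real timing effect, with choosers entering the window only in the Intervention block and g = 0.** The move recovers T. The as-randomised contrast is again (1 − f)T.

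**As randomised.** In every no-effect scenario, bias is about 0 min and rejection about 5%.

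**Group sizes.** Moving 5 or 10 of 25 gives 30 versus 20 or 35 versus 15. Power for 78 min, by the plan's own type of calculation, falls from 0.904 to 0.893 or 0.850.

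**The case against.** The strongest reply is that nothing is lost. Every Aim 2b outcome is already modelled with the three randomised groups under Aims 1, 2 and 2a, so a randomised B versus C contrast can be drawn from those models. On this view the as-slept grouping is an openly stated addition to an exploratory, optional analysis. It also has a rationale: Aim 2b asks about timing itself, and the as-randomised contrast is diluted when part of C sleeps in B's window.

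The Aim 2a text compares Baseline with Intervention data across the groups, which suggests that the intended test is change by group. On that reading stable gaps cancel and the main-effect figures do not apply. Section II says night workers typically sleep in the morning, so f may be small and the bias trivial. Group B's clock times imply a window for C, and leaving Group B non-compliers in B is ordinary as-randomised handling.

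Much of this stands as a limit on size and scope. The change reading is the more natural one, a small f is plausible, and an as-slept analysis has a place. It does not remove the fault. The only analysis the plan names for timing is the regrouped one, under a label that is no longer true. A gap in change biases it on either model term. Group B's clock times come with no stated tolerance for classifying C. Keeping B as randomised while sorting C by behaviour gives a contrast that is neither as randomised nor as slept.

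**Conclusion.** The concern holds. As written, the Aim 2b timing test is a post-randomisation comparison labelled as a randomised one, and no as-randomised B versus C test is named for that aim.

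The size cannot be fixed from the documents. For f from 0.1 to 0.4 and a gap in change of 20 to 60 min, at correlation 0.5, the bias on condition-by-block runs from about 4 to 34 min and false-positive rates from about 5% to 22%. Below that share it is small. The sign reverses if choosers do worse than others. If choosers do not differ, the false-positive rate stays near 5%.

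The consequence is confined to an exploratory aim; the models for Aims 1, 2 and 2a keep the randomised groups. It should still be corrected before analysis, because any claim about timing apart from time in bed would rest on this comparison.

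**What to change.** In the Aim 2b paragraph of Section VI:

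1. Make B versus C as randomised, with every Group C participant kept in C, the Aim 2b analysis.
2. Name the condition-by-block (or condition-by-night) contrast as the timing test.
3. Keep the as-slept comparison as a supplement labelled non-randomised, and do not call its factor randomisation group.
4. For that supplement, set the clock-time definition for classifying sleep episodes before the data are examined, and state how Group B participants who slept outside their window are handled.

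This takes a few sentences and no new data. The price is that the as-randomised contrast estimates the effect of assigning the timing, diluted to (1 − f)T (for example 0.8T at f = 0.2). Scenario 4 in the working is the reason to retain the supplement.

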#### **VI.d. Power analysis**

For the Field Trial we plan to enroll up to 100 participants, with at least 25 participants per group for three groups including A) control group (ad lib sleep); B) 8-h afternoon-evening sleep timing group; C) 8-h free sleep group. For the Shift Worker Survey, we aim to enroll up to 1,000 participants. In the Focus Groups we plan to enroll up to 60 participants, ~30 participants who complete the Field Trial and ~30 participants who complete the Shift Worker Survey.

Our sample size calculations for the Field Trial are based on the preliminary data from our laboratory study (6) comparing the ad lib sleep group with the 8-h scheduled afternoon-evening sleep group, and using total sleep time (TST) and Fragmentation Index (FI) after 2 nights as the outcome measures of interest. For TST, 25 participants per group will give us the power to detect a difference of as few as 78 minutes between groups ( $\alpha=0.05$ ,  $\beta=0.9$ , assumed  $\sigma=84.4$  min), a difference much smaller than that observed in our preliminary study ( $221.4 \pm 84.4$  vs.  $403 \pm 58.5$  min). For FI, 25 participants per group will give us the power to detect a difference of 37 in the fragmentation index (assumed  $\alpha=0.05$ ,  $\beta=0.9$ , assumed  $\sigma=39.9$ ), a smaller difference than that observed in our preliminary study ( $73.3 \pm 39.6$  vs.  $35.2 \pm 20.03$ ).

Our sample size calculations for the Shift Worker Survey are based on multivariable analysis. With at least 500 participants, we will have 90% power to detect an odds ratio of 1.51 for any continuous factor with one standard deviation difference, or 2.10 for any binary factor (yes vs. no) with a two-sized z-test at alpha=0.05 level, assuming the variance explained by other factors in the same model is 0.2.

Our sample size of 30 participants for the Focus Groups were selected to solicit qualitative information from approximately half of the Field Trial participants who were randomized to a sleep intervention, and from approximately 10% of the Shift Worker Survey participants who report being unable to adopt an 8-h sleep schedule when working night shifts.

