**III.a.b. Shift Worker Survey inclusion/exclusion criteria and recruitment methods:** We aim to enroll up to 1,000 participants in the Shift Worker Survey. We will use internet and newspaper advertisements and flyers to recruit employed individuals (20 or more hours per week) whose work includes overnight shifts [six or more consecutive hours between 10 pm and 7 am], with a minimum criterion of at least 4 night shifts a month. Both women and men aged 18 and older will be studied. We will recruit among all occupations, and include participants from throughout New England to take part in this web-based survey. Additionally, we will post notices in local hospitals and advertise on the Massachusetts Nursing Association Facebook page.

**III.a.b. Focus Group inclusion/exclusion criteria and recruitment methods:** We aim to enroll up to 60 individuals in virtual Focus Groups.

All health care workers in the Field Trial who are randomized to the 8-h afternoon/evening or the 8-h free sleep intervention groups will be invited to attend a virtual Focus Group discussion by secure videoconferencing

(via HIPAA-compliant & MGB-approved Zoom) so that we can gain in-depth information on the acceptability of the fixed 8-h sleep schedule from participants' perspective. We plan to enroll up to 30 individuals who take part in the Field Trial in Focus Groups. Virtual Focus groups will include health care workers who comply with the 8-h sleep intervention as well as those who do not comply or who withdraw from the intervention so that we may learn about facilitators and barriers for compliance with the fixed 8-h sleep schedule.

In addition to the health care workers who took part in the Field Trial, we will invite night shift workers who complete the Shift Worker Survey but indicate their inability to comply with a fixed 8-h sleep schedule to attend a remote Focus Group discussion. We expect that approximately half of the Shift Work Survey participants will indicate that they cannot comply with a fixed 8-h sleep schedule. We will email randomly chosen individuals from this cohort, inviting them to participate, until we achieve an enrollment of 30 individuals to gain in-depth information on challenges and barriers to adhering to an 8-h sleep schedule, as well as their opinions on what resources and facilitators at individual, interpersonal, and organizational levels could be used to promote use of such sleep strategies.

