**General Methods for Shift Worker Survey.** To examine factors related to individual differences in the ability to adopt the sleep strategy, we will use a web-based survey consisting of ~70 questions developed and administered using REDCap. REDCap is a free, secure, web-based application for building and managing online surveys and databases. The complete questionnaire will take approximately 20-30 minutes to complete.

To understand the individual differences in sleep patterns adopted by shift workers, both in timing and in duration, and their ability to adjust sleep schedules, we will include demographic factors, circadian factors, questions of sleep in general and specific to night shifts, use of countermeasures, questions about non-work and work activities, and quality of life. We have selected factors which have been reported to be associated with inter-individual differences in adaptability to shift work and/or vulnerability to sleep loss, and therefore may contribute to the ability to adopt different sleep schedules in order to understand the barriers to achieving an 8-h sleep episode when working nights (72-76, 78, 117-119).

We will use questionnaires widely used in sleep research to assess morningness/circadian preference (120), flexibility of sleeping habits, vigor [i.e., the ability to overcome drowsiness (121, 122)], screening for shift work disorder (123), and qualty of life (124). We will also examine environmental factors (e.g. barriers/facilitators) that may be related to the feasibility of an individual being able to adopt an 8-h sleep episode, such as work hours, second jobs, work schedule (rotation and speed of rotation), type of occupation, commute time, and home sleep environment (noise, light).

For individuals who may not have access to a computer, we will provide a paper copy of the questionnaire to fill out and return.

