**Analysis of the Shift Worker Survey.** (Specific Aim 3). The initial scoring of standard questionnaires and processing of data will be calculated automatically in REDCap. Descriptive analyses for all factors of interest will be calculated, as well as the reported ability to adhere to an 8-h free sleep/ 8-h afternoon-evening sleep schedule. To understand what individual differences contribute to shift workers' sleep patterns and ability to comply with an 8-h sleep schedule, we may conduct inferential statistics including bivariate and multivariate analyses on factors related to their ability to adopt the 8-h free sleep/8-h afternoon-evening sleep. Bivariate analyses (ANOVA and cross-tabulation) will be used to interpret the correlation between each factor and the outcome (ability to adhere to 8-h afternoon-evening sleep; ability to adhere to 8-h free sleep; inability to adhere to 8-h sleep).

Multivariable analysis (logistic regression analysis) and multivariate analysis (for example, structure equation modeling) may be used to test potential predictors of the outcome.

**Focus Group analysis** (Specific Aim 3). Data from this aim will be qualitative in nature. Focus group transcripts will be imported into NVivo11 or similar software for analysis. We will reorganize, reduce, and categorize the qualitative data based on common themes, and use content analysis to identify recurrent themes (157, 159). The code and quotes will be discussed by the research team to resolve discrepancies through interpretive discussions, consensus building, and refinement of code definitions as needed. The data will be independently coded by the investigators and compared to achieve consistency and conformability. The research team may send the focus group analysis results to participants to verify the codes and confirm the interpretive validity (159).

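### The Shift Worker Survey's 90% power for an odds ratio of 2.10 at 500 participants is claimed for every yes/no factor, but it fails for unevenly split factors, and the assumptions behind it are not stated

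*Combined protocol and SAP*

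**What the plan says.** Section VI.d (Power analysis) bases the survey's sample size on multivariable analysis. With at least 500 participants it claims 90% power for an odds ratio of 1.51 per standard deviation of a continuous factor, "or 2.10 for any binary factor (yes vs. no) with a two-sized z-test at alpha=0.05 level". The allowance made for the remaining covariates is given as well: "assuming the variance explained by other factors in the same model is 0.2". No factor prevalence, outcome category or outcome rate accompanies these figures.

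Other sections bear on the claim:

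- Section VI (Analysis of the Shift Worker Survey) lists three outcome categories: "ability to adhere to 8-h afternoon-evening sleep; ability to adhere to 8-h free sleep; inability to adhere to 8-h sleep". It says logistic regression may be used.
- Section III (Focus Group recruitment) gives one outcome rate, for a recruitment purpose: "We expect that approximately half of the Shift Work Survey participants will indicate that they cannot comply with a fixed 8-h sleep schedule".
- Section III also sets the ceiling: "We aim to enroll up to 1,000 participants in the Shift Worker Survey".
- Aim 3 in section II is to "examine how demographic (e.g., sex) and other factors (e.g., occupation) impact this adoptability". Section V (General Methods for Shift Worker Survey) adds factors such as "work hours, second jobs, work schedule (rotation and speed of rotation), type of occupation, commute time".

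**The concern.** For a binary predictor in logistic regression, power depends on how the sample splits on the factor and on the outcome rate. A single detectable odds ratio therefore cannot hold for every yes/no factor. The sentence claims that it does, and it leaves out the values needed to see where it holds.

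Aim 3 is about which factors influence ability to adopt the schedule. Several of the listed factors could be unevenly split, although the documents give no frequencies. If survey enrolment ends near 500, a reader of section VI.d could take an inconclusive result for an uncommon factor as having had 90% power against 2.10, when the true figure could be well below that.

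**Working it through.** **Inputs**

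- From section VI.d: n = 500, odds ratio 2.10, two-sided alpha 0.05, R-squared 0.2. Effective size N = 500 × (1 − 0.2) = 400.
- Model: logistic regression (section VI).
- Factor prevalence B: not in the documents; assumed 10-50%.
- Outcome rate without the factor, P1: not in the power paragraph; assumed 20-50%. Section III's figure of about half is tried separately as an overall rate.

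**Formula** (Hsieh, binary covariate)

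P2 = 2.10·P1 / (1 − P1 + 2.10·P1); P = (1 − B)·P1 + B·P2

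z = { √[N(P1 − P2)²(1 − B)] − 1.96·√[P(1 − P)/B] } / √[P1(1 − P1) + P2(1 − P2)(1 − B)/B]; power = Φ(z)

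**Step 1: reproduce the plan's figure.** Take B = 0.5 and P1 = 0.20. Then P2 = 0.42/1.22 = 0.344 and P = 0.272. z = (2.040 − 1.234)/0.621 = 1.299, so power is **90.3%**.

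For the companion continuous figure, OR = exp{(1.96 + 1.2816)/√[400·P(1 − P)]}. This gives 1.50 at P = 0.20, 1.51 at P = 0.191 and 1.38 at P = 0.50. A rate near 20% therefore fits both stated odds ratios approximately. This is a back-fit, not something the protocol states.

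**Step 2: change only the prevalence, keeping P1 = 0.20.**

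- B = 0.2: z = (2.581 − 1.841)/1.031 = 0.717, power **76.3%**.
- B = 0.1: z = (2.737 − 2.544)/1.480 = 0.131, power **55.2%**.

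**Step 3: vary the outcome rate** (n = 500, OR 2.10, factor raises the odds).

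| Factor prevalence | P1 = 20% | 30% | 40% | 50% |
|---|---|---|---|---|
| 50% | 90.3% | 94.9% | 95.9% | 95.3% |
| 30% | 85.5% | 91.1% | 92.4% | 91.4% |
| 20% | 76.3% | 82.8% | 84.2% | 82.4% |
| 10% | 55.2% | 60.3% | 60.7% | 57.2% |

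Scanning P1 from 1% to 99%, power peaks at 84.3% for the 20% factor and 61.0% for the 10% factor. No outcome rate brings either to 90%.

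The prevalences that do reach 90% are about 44-54% at P1 = 20%, 28-71% at 30%, 26-74% at 40% and 28-73% at 50%.

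With the overall outcome rate set to 50%, power is 96% (50/50 factor), 92% (30%), 83% (20%) and 58% (10%), the same in either direction.

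**Step 4: what 90% power would take** (P1 = 20-50%).

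| Factor prevalence | OR with 90% power at n = 500 | n for 90% at OR 2.10 | Power at n = 1,000, OR 2.10 |
|---|---|---|---|
| 20% | 2.25-2.44 | about 600-750 | 96.0-98.7% |
| 10% | 2.93-3.15 | about 1,055-1,316 | 81.5-88.4% |

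At an overall rate of 50%, the odds ratios with 90% power at n = 500 are about 2.27 (20% factor) and 3.05 (10% factor).

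**Step 5: direction.** With a 50/50 factor and P1 = 20%, power for an odds ratio of 1/2.10 is 74%, against 90% for 2.10. If the complementary outcome is coded (P1 = 80%), the two figures swap.

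**The case against.** The strongest reply is that nothing has been miscalculated. The 90% reproduces for an even factor, which is a common reference case, and the 20% and 10% prevalences are the reviewer's choice. At outcome rates of 30-50% without the factor, any prevalence from about 28% to 71% reaches 90%. If about half is the relevant overall rate, the stated figures are conservative for continuous factors (1.38 would do) and for even binary ones (1.92). The 500 is a floor, up to 1,000 may enrol, the inferential analyses are optional in wording, and no decision rule rests on this power.

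Most of that stands and limits the consequence. It does not make the sentence true: the text covers every binary factor and nowhere mentions an even split. Even at 1,000 participants a 10% factor stays below 90%.

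Three stronger readings are tempting, and the documents do not support them:

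- *The inferred 20% contradicts the half expected in section III.* It need not. The half concerns inability to comply, while 20% could describe another of the three outcome categories.
- *The focus-group fraction exposes an inconsistent rate.* Section VI.d describes 30 people drawn "from approximately 10% of the Shift Worker Survey participants who report being unable to adopt an 8-h sleep schedule when working night shifts". Half of 500 is 250, and 30/250 = 12%, which is compatible with that rounding.
- *The plan is weak against protective factors.* The asymmetry in step 5 depends on outcome coding and on a rate the protocol does not state.

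**Conclusion.** The claim is wrong as written, because of its scope and its missing assumptions; the underlying calculation reproduces. At 500 participants and an odds ratio of 2.10, a factor held by 20% falls about 6 to 14 percentage points short of 90% (90 − 84 to 90 − 76), and one held by 10% about 29 to 35 points short (90 − 61 to 90 − 55). These sizes rest on the Hsieh formula with R-squared 0.2, a factor that raises the odds, and assumed outcome rates of 20-50% without it. That some shortfall exists at these two prevalences does not depend on the outcome rate. Whether any survey factor is in fact that uncommon cannot be told from the documents. A reader might infer that the survey as a whole is underpowered; that does not follow, since roughly even factors have the stated power at 500 under these assumptions. The randomised Field Trial has its own calculation and is not touched.

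**What to change.** In section VI.d:

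1. Replace the reference to every binary factor with the factor prevalence, the section VI outcome category and the outcome rate actually assumed. Say whether that rate is overall or among those without the factor.
2. Limit the 90% to factors about that evenly split.
3. Add the odds ratios with 90% power at 500 participants for less even factors: about 2.25-2.44 (20% factor) and 2.93-3.15 (10% factor) at rates of 20-50% without the factor. If the outcome is inability at about half overall, use about 2.27 and 3.05.
4. If the assumed rate is well away from 50%, note that the 90% applies to one direction of effect under the chosen outcome coding.

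The cost is protocol wording only. No extra participants are needed; the stated figure becomes less favourable for uncommon factors.
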